5.3.1 Potential Risks

As Anakinra is currently used for treating autoimmune diseases it has a well-established side effect profile. There are not expected to be any specific side effects that relate to refractory moderate to severe CRPS with the exception of possible increases in pain, and new pain at the subcutaneous injection side. The latter is a relevant potential risk as CRPS is a post-traumatic condition and an injection constitues a very minor trauma; this risk will be carefully monitored. Injection sites will be rotated to minimise this risk. Of note, in the CRPS literature there are to our knowledge no reports about development of new CRPS at subcutaneous injection sites in patients with established refractory CRPS.

Anakinra can cause ARs such as:

- 1. Worsening of CRPS symptoms (presumed risk)
- 2. New CRPS symptoms at the IV injection site (presumed risk)
- 3. Nausea, vomiting, diarrhoea and abdominal pain (10%)
- 4. Headache (12%)
- 5. Joint pain (0-12%)
- 6. Flu like symptoms
- 7. Infection, bruising and swelling at the injection site

The most serious side effect include infections and neutropenia but these are rare. There is a risk of hypersensitivity at 0.1-1% but severe reactions are rare.

Currently with the Covid-19 pandemic there is a potential risk if participants are infected taking anakinra. These risks are not fully known and careful judgement must be made to balance the risk of potential infection with possible benefits. Of note, Anakinra is currently used in a number of clinical trials to treat the systemic immune response to Covid-19 infection. There is no contra-indication to the current vaccines against Covid-19 for patients on anakinra as these vaccines are not live.

Mitigation of risk will be done by increased follow up and surveillence compared with standard follow up with participants on Anakinra. While these ARs are known or specifically assumed side effects of anakinra, all serious and non-serious AEs will be reported (see section 13).

Investigators will be made aware of any changes in the Summary of Product Characteristics (SmPC) but the protocol will not need to be amended unless it directly affects the conduct of the study.

This trial is categorised Type B (somewhat higher than the risk of standard medical care) as per the risk-adapted approach to clinical trials adopted by the MHRA.

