13.1 Terms and Definitions

Adverse Event (AE)

Any untoward medical occurrence in a patient or clinical trial subject administered a medicinal product and which does not necessarily have a causal relationship with this treatment.

An AE can therefore be any unfavourable and unintended sign (including an abnormal laboratory finding, for example), symptom or disease temporally associated with the use of a medicinal product, whether or not considered related to the medicinal product.

Adverse Reaction (AR)

Any untoward and unintended response to an IMP related to any dose administered.

Condition Specific Adverse Event

Persistent pain at injection site (greater than 1 week) of at least moderate intensity (5 or greater on a 0-10 NRS scale) and increase in CRPS associated pain(>=2points NRS), ongoing for >1 month.

Serious Adverse Event (SAE)

Any untoward medical occurrence or effect that at any dose results in death, is life-threatening, requires hospitalisation or prolongation of existing hospitalisation, results in persistent or significant disability or incapacity, or is a congenital anomaly or birth defect.

Serious Adverse Reaction (SAR)

An AR which meets the definition of serious (see Section 13.2) is a SAR. A SAR event that has been assessed as 'expected' (see Section 13.5 Expectedness) according to the Reference Safety Information (RSI) (see below) will remain classified as a SAR only, however some SARs that are considered 'unexpected' will be further classified as a Suspected Unexpected Serious Adverse Reaction (SUSAR) (see below).

Suspected Unexpected Serious Adverse Reaction (SUSAR)

An AR that is classed in nature as serious and "unexpected" (i.e. not listed within the RSI approved for the trial by the MHRA and current at the time of onset of the SUSAR).

Reference Safety Information (RSI)

The information used for assessing whether an AR is expected (see section 13.5). This is contained in the SmPC for the product and must be approved for use by the MHRA. The RSI used to assess the expectedness of a SAR must be the current approved version at the time of onset of the SAR. The RSI for this trial is defined in section 13.5.1.

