13.7 Notes on Safety Event Recording

The following events must be recorded for the purposes of the trial:

- An exacerbation of a pre-existing illness
- An increase in frequency or intensity of a pre-existing episodic event/condition

- A condition (even though it may have been present prior to the start of the trial) detected after trial drug administration
- Continuous persistent disease or symptoms present at baseline (0 day) that worsens following the administration of the study/trial treatment
- Laboratory abnormalities that require clinical intervention or further investigation (unless they are associated with an already reported clinical event).
- Abnormalities in physiological testing or physical examination that require further investigation or clinical intervention
- Injury or accidents
- Pregnancy (See section 13.8 for more details)
- Weight loss of ≥4% within 4 months

Do not record:

- Medical or surgical procedures the condition which leads to the procedure is the AE
- Pre-existing disease or conditions present before treatment that do not worsen
- Situations where an untoward medical occurrence has occurred e.g. cosmetic elective surgery¹
- Overdose of medication without signs or symptoms*2
- The disease being treated or associated symptoms/signs unless more severe than expected for the participant's condition

*N.B. If overdose occurred **with** resulting signs and symptoms that meet the protocol criteria for AE/AR/SAE/SAR/SUSAR then they should be reported accordingly (see section 13.12 for more information) and the overdose highlighted to the LCTC team.

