13.11 Reporting Safety Events to the LCTC

All safety events (whether or not assessed as serious / related / expected) should be recorded on an AE Form.

Safety events which are assessed as "serious" must **also** be recorded in more detail on SAE Forms; a single form is used for each individual event (i.e. a single diagnosis), though multiple symptoms can be recorded. Each SAE should have a corresponding record on the participant's AE form. Where additional information is received by site after initial submission to LCTC, this should be provided on a follow-up form within 5 days. SAE Forms collect data regarding the nature of event, date of onset, severity, corrective therapies given, outcome and causality; all serious events reported to LCTC will be reviewed by the CI or other Medical Reviewer, and assessed for causality and expectedness.

Follow-up After Adverse Events

All reportable AEs should be followed until satisfactory resolution or until the investigator responsible for the care of the participant deems the event to be chronic or the participant to be stable.

When reporting "serious" safety events the investigator responsible for the care of the participant should apply the following criteria to provide information relating to event outcomes:

- resolved
- resolved with sequelae (specifying with additional narrative)
- not resolved/ongoing
- ongoing at final follow-up
- fatal or unknown.

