13.12 Investigator Reporting Responsibilities

The PI is responsible for ensuring that all safety events requiring recording on this study (see section 13) which the local research team becomes aware of are reported to LCTC. It is the responsibility of an appropriately medically qualified person as recorded on the Delegation Log to assess the seriousness and causality of events. When documenting any AEs, the correct medical terminology **must** be used.

All safety events must be recorded on an AE form and a copy of the form transferred to LCTC within seven days of the site team becoming aware of the event.

Safety events which meet the definition of "serious" must be reported in more detail to the LCTC on an SAE form and reported **immediately and in no circumstances later than 24 hours from becoming aware** unless the SAE is specified in the protocol as not requiring immediate reporting (see Section 13).

The SAE form should be completed by an appropriately delegated member of the research team; the assessments of seriousness and causality must be performed by an appropriately medically qualified person. Minimum reporting information must be provided in initial reports for all studies.

N.B. In the absence of a delegated medically qualified person the form should be completed and signed by an alternative member of the research site trial team and submitted to the LCTC. As soon as possible thereafter the responsible investigator should check the SAE form, make amendments as appropriate in line with GCP, sign and re-send to the LCTC. The initial report shall be followed by detailed follow-up reports as appropriate.

Safety events should be reported to the site R&D team in accordance with local policy.

Separate guidance are provided regarding appropriate completion of serious safety events.

REPORTING AN INITIAL OR FOLLOW-UP SAE

The investigator should ensure the actions below are completed for all reportable SAEs:

- 1) Research sites should telephone the appropriate trial team on [contact]** to advise that an SAE report will be submitted as soon as possible.
- 2) The SAE form should be emailed securely to [contact] within 24 hours of becoming aware of the event. If email is not available please contact the trial team on [name].
- 3) The responsible investigator must notify their R&D department of the event (as per standard local governance procedures).

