25.1.2.2 Safety

The frequency and proportion of participants, denominator used as the number registered, who have experienced the below will be summarised:

persistent pain (greater than one week) at the injection site of at least moderate intensity (≥

5 on a 0-10 NRS scale)

• a substantial CRPS pain increase of  $\geq$  2 points NRS, ongoing for more than 1 month despite

and from the time of pain related treatment stop.

SARs

The substantial pain increase will be calculated as: CRPS pain at day X – CRPS pain at day (X-30), where X is >30. Persistent pain will be derived from the pain dairies and adverse events. Both substantial pain increase and persistent pain are collected throughout the trial as Adverse events and are particularily asked about at each visit (see forms 5 – Telephone Follow up, 6 Follow up and 7 Final Telephone follow up). The yes/no response at each visit and the derived substantial pain increase/persistent pain will

both be used to ensure all events are captured.

If 3 or less patients report persistent pain or substantial pain increase across the first 10 participants

registered this criteria will have been met.

However, stopping will be considered if 30% or more of study participants experience an SAR in the first 12 months of recruitment.

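### Protocol 13.7 appears to have lost the word *not* from its do-not-record list, and the SAP's primary outcome lacks the derived pain check used for progression

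*Protocol*

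**What the plan says.** **Recording instruction.** Protocol 13.7 gives one list of events that must be recorded and one of things not to record. The second list includes "Situations where an untoward medical occurrence has occurred e.g. cosmetic elective surgery". Protocol 13.1 defines an adverse event as "Any untoward medical occurrence in a patient or clinical trial subject administered a medicinal product", with no causal link required. Protocol 13.11 says "All safety events (whether or not assessed as serious / related / expected) should be recorded on an AE Form", and 13.12 says "All safety events must be recorded on an AE form and a copy of the form transferred to LCTC within seven days" of the site learning of the event. Protocol 5.3.1 promises reporting of serious and non-serious events alike.

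**Primary outcome.** SAP 25.2.2.1 defines it as the share of registered patients with neither a serious nor a condition-specific adverse event. The condition-specific events are injection-site pain of 5 or more lasting over a week, and a CRPS pain rise of at least 2 NRS points lasting over a month. They are identified from the premature discontinuation and withdrawal forms and Forms 5, 6 and 7, with details from the adverse event and serious event forms. No calculated pain event is mentioned.

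**Progression criteria.** For nearly the same pain events, SAP 25.1.2.2 goes further. "Persistent pain will be derived from the pain dairies and adverse events", and "The substantial pain increase will be calculated as: CRPS pain at day X" minus the score 30 days before. It adds that "The yes/no response at each visit and the derived substantial pain increase/persistent pain will" be used together so that none is missed.

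**The concern.** The trial's primary outcome is safety, so what sites record and how events are found determine the main result.

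The 13.7 bullet is an instruction to sites, and as printed it says the reverse of what the rest of section 13 requires.

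The SAP gap concerns ascertainment. The CRPS component of the primary outcome is a numeric threshold on a score collected throughout the trial, yet the primary derivation does not compare the scores with the threshold. It relies on someone answering yes on a form. For progression, the SAP judges that form answers should be backed by derived events. For the primary outcome it does not. Because the denominator is all registered patients, an unreported qualifying event moves a participant into the event-free numerator, so the error can run only in the favourable direction.

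**Working it through.** The plan gives no figure to reproduce. The check is mainly textual, with short arithmetic for scale.

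**1. The 13.7 bullet.** An adverse event is an untoward medical occurrence (13.1). The bullet tells sites not to record situations where one has occurred. Taken literally, nothing is recordable, against 13.11, 13.12 and the must-record list in 13.7 itself. With *not* inserted, the bullet excludes planned procedures with no untoward event behind them. That fits the cosmetic-surgery example and matches 13.2, which does not treat elective admissions for an unworsened condition as serious. Only the second reading is coherent.

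**2. Sources of pain events in the SAP.**

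| Event | Progression (25.1.2.2) | Primary (25.2.2.1) |
|---|---|---|
| Injection-site pain | Diaries, adverse events, visit yes/no answers | Forms only |
| CRPS pain rise | Calculated difference (source not named), adverse events, visit yes/no answers | Forms only |

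SAP 25.2.2.2 adds no derived event, and Table 25-1 links diaries to secondary outcomes only.

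**3. Scores available for a check.** Protocol Table 4 schedules a CRPS pain NRS at every visit and call from baseline. Diaries are weekly to day 90, daily to day 120 and weekly to day 180, but Table 4 last marks diary issue and collection at day 120.

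**4. Scale.** One missed participant with no other qualifying event: 1/30 = 3.3 points. If one to three were missed (an assumption; the documents give no rate): 1/30 to 3/30, or 3.3 to 10.0 points.

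**5. What a derived check can see, taking a month as 30 days.**
- Nominal contacts to day 120 fall on days 0, 14, 30, 44, 60, 74, 90, 104 and 120. Three consecutive contacts span 14 + 16 = 30 days, which is not more than 30. Four span 14 + 16 + 14 = 44 or 16 + 14 + 16 = 46 days.
- In the weekly diary phase, six consecutive entries are needed: 5 × 7 = 35 days.
- A rise starting on day s lasts more than 30 days by day 180 if s + 31 ≤ 180, so s = 0 to 149 (150 days). By day 120 it needs s + 31 ≤ 120, so s = 0 to 89 (90 days). Scores to day 120 can therefore confirm at most 90/150 = 60% of possible onset days (92/152 = 60.5% for a 28-day month, 89/149 = 59.7% for 31 days). This counts days; it is not a probability.
- Later onsets rest on form answers, any weekly entries returned and the day 180 score. Table 4 marks that score, although the telephone list in 10.7 mentions pain assessment only to day 120.

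**6. Why the progression formula should not be reused.** It compares two readings 30 days apart, with X above 30, so day 30 minus day 0 is never taken. Taking X at clinic visits:

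| NRS at days 0, 30, 60, 90, 120 | Differences at X = 60, 90, 120 | Flag | Sustained rise of 2 or more over baseline? |
|---|---|---|---|
| 6, 7, 8, 8, 8 | 1, 0, 0 | No | Yes, day 60 to day 120 |
| 6, 8, 8, 8, 8 | 0, 0, 0 | No | Yes, day 30 to day 120 |
| 6, 6, 8, 6, 6 | 2, −2, 0 | Yes | No, a single reading |

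It can miss sustained rises and flag isolated ones.

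**The case against.** On 13.7, the slip corrects itself in context, and no harm to any participant or estimate is shown. That stands. The bullet also carries a footnote mark whose text is not in the extract, so the source file needs checking. A reader might infer that sites are being told to suppress adverse events and that the primary outcome is under-counted as a result. The documents do not support that: the example, the must-record list, 13.11 and 13.12 all point the other way. Nor is the last bullet of the list, on the disease being treated, a defect. It carries its own exception for symptoms more severe than expected, and the must-record list covers exacerbation and worsening.

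On the SAP, a reader might infer that a diary check on CRPS pain exists for progression and was dropped for the primary outcome. That goes too far. SAP 25.1.2.2 names diaries only for persistent pain, which in that section is the injection-site component. It does not state the source for the CRPS rise, and the visit NRS is just as available.

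Much is also handled in practice. Protocol 10.7 has sites assess pain from the diaries at clinic visits, and both events are asked about on Forms 5, 6 and 7, which feed the primary derivation. This makes missed events less likely, and it is why the effect is probably small.

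Finally, the progression criteria are a guide, their CRPS event is tied to stopping pain-related treatment, and a wider net for monitoring is defensible. That explains a difference in definition. It does not explain leaving a numeric threshold in the primary outcome unchecked against scores already collected.

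**Conclusion.** Both parts hold, and both are minor.

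The 13.7 bullet is a drafting error, provided the source file reads as the extract does. No effect on results is claimed.

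The primary derivation relies on reported events alone for a component defined by a numeric score. Any qualifying CRPS rise missed by the forms inflates the event-free proportion, by 3.3 points per participant if 30 are registered and the participant has no other qualifying event. How many would be missed cannot be estimated from the documents.

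**What to change.** **Protocol 13.7.** After checking the source file and footnote, insert *not* before *occurred*. Optionally, add a sentence saying that events meeting the condition-specific definition in 13.1 always go on the adverse event form.

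**SAP 25.2.2.1.** Add a derived check for the CRPS component:
- Flag as a candidate any rise of at least 2 NRS points above the Form 4 baseline, sustained for more than a month. The primary definition names no reference; Form 4 is what SAP 25.2.3.2.1.1 already uses for pain change. State how many days make a month and how many consecutive raised scores are required.
- Use the NRS scores scheduled at each visit and call in Table 4, supplemented by returned diaries. Use weekly entries after day 120 only where they come back.
- Reconcile candidates with Forms 5, 6 and 7 and the adverse event forms before data freeze, and count confirmed events in the primary outcome. Confirmation matters because the baseline is a single 24-hour score and will produce some false flags.
- Do not carry over the 30-day difference formula or the progression rule's treatment-stop condition.
- Leave injection-site pain on the forms, since the diary is not shown to capture it.

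**Cost.** One word in the protocol, one extra derivation and one query listing. No new data are needed. The event-free proportion may fall slightly.

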13.8 Reporting of Pregnancy

If pregnancy occurs during either the intervention or follow up period of the trial this must be notified to the LCTC using the appropriate CRF within 24 hours of the research team becoming aware. The pregnancy must be followed up by the site research team until childbirth and reported to LCTC.

Any pregnancies which result in a safety event assessed as "serious" (e.g. birth defect) must also be reported separately on the appropriate Safety Event CRFs in accordance with processes described in section 13. All pregnancies and outcomes reported to LCTC will be notified to the study Sponsor and monitored by trial oversight committees.

13.9 Notification of Deaths

If the research team become aware of the death of a participant (whether related to the trial or not) this should be notified to the LCTC using the appropriate CRF within 24 hours of becoming aware.

13.10 Reporting Procedures

All safety events which are recorded for the study should be reported following the procedures detailed below. The occurrence of a safety event may come to the attention of research staff during routine study visits, from the participant's notes, directly from the participant or by other means. Note that reporting procedures vary dependent on the nature of the incident (i.e. "serious" events are to be reported to LCTC in an expedited manner). Any questions concerning AE reporting should be directed to the LCTC in the first instance. A flowchart is given below to aid in determining reporting procedures for different types of AEs.

[figure not shown]

Figure 2: Flowchart for Site Reporting Requirements of Adverse Events

13.11 Reporting Safety Events to the LCTC

All safety events (whether or not assessed as serious / related / expected) should be recorded on an AE Form.

Safety events which are assessed as "serious" must **also** be recorded in more detail on SAE Forms; a single form is used for each individual event (i.e. a single diagnosis), though multiple symptoms can be recorded. Each SAE should have a corresponding record on the participant's AE form. Where additional information is received by site after initial submission to LCTC, this should be provided on a follow-up form within 5 days. SAE Forms collect data regarding the nature of event, date of onset, severity, corrective therapies given, outcome and causality; all serious events reported to LCTC will be reviewed by the CI or other Medical Reviewer, and assessed for causality and expectedness.

Follow-up After Adverse Events

All reportable AEs should be followed until satisfactory resolution or until the investigator responsible for the care of the participant deems the event to be chronic or the participant to be stable.

When reporting "serious" safety events the investigator responsible for the care of the participant should apply the following criteria to provide information relating to event outcomes:

- resolved
- resolved with sequelae (specifying with additional narrative)
- not resolved/ongoing
- ongoing at final follow-up
- fatal or unknown.

13.12 Investigator Reporting Responsibilities

The PI is responsible for ensuring that all safety events requiring recording on this study (see section 13) which the local research team becomes aware of are reported to LCTC. It is the responsibility of an appropriately medically qualified person as recorded on the Delegation Log to assess the seriousness and causality of events. When documenting any AEs, the correct medical terminology **must** be used.

All safety events must be recorded on an AE form and a copy of the form transferred to LCTC within seven days of the site team becoming aware of the event.

Safety events which meet the definition of "serious" must be reported in more detail to the LCTC on an SAE form and reported **immediately and in no circumstances later than 24 hours from becoming aware** unless the SAE is specified in the protocol as not requiring immediate reporting (see Section 13).

The SAE form should be completed by an appropriately delegated member of the research team; the assessments of seriousness and causality must be performed by an appropriately medically qualified person. Minimum reporting information must be provided in initial reports for all studies.

N.B. In the absence of a delegated medically qualified person the form should be completed and signed by an alternative member of the research site trial team and submitted to the LCTC. As soon as possible thereafter the responsible investigator should check the SAE form, make amendments as appropriate in line with GCP, sign and re-send to the LCTC. The initial report shall be followed by detailed follow-up reports as appropriate.

Safety events should be reported to the site R&D team in accordance with local policy.

Separate guidance are provided regarding appropriate completion of serious safety events.

REPORTING AN INITIAL OR FOLLOW-UP SAE

The investigator should ensure the actions below are completed for all reportable SAEs:

- 1) Research sites should telephone the appropriate trial team on [contact]** to advise that an SAE report will be submitted as soon as possible.
- 2) The SAE form should be emailed securely to [contact] within 24 hours of becoming aware of the event. If email is not available please contact the trial team on [name].
- 3) The responsible investigator must notify their R&D department of the event (as per standard local governance procedures).
- 4) The participant must be identified by trial number, age and initials **only**. The participant's name **should not** be used on any correspondence.
- 5) SAEs must be subsequently followed up in line with the processes below:
 - Follow up must continue until clinical recovery is complete and laboratory results have returned to normal, or until the event has stabilised (see Section 13). N.B. Follow-up may continue after completion of protocol treatment if necessary.
 - Follow-up information is noted on a new SAE form to be transferred securely to the LCTC as soon as more information becomes available
 - Tick the appropriate box on the new SAE form to identify the type of report; this is dependent on resolution status of the SAE e.g. follow-up / final.

Patient safety incidents that take place in the course of research should be reported to the National Reporting and Learning System (NRLS) by each participating NHS Trust in accordance with local reporting procedures. This also includes reporting any NIMPs.

